7.3.1.2. Subgroup Analysis

There is no planned subgroup analysis.

7.3.1.3. Multicenter Studies

Not applicable.

7.3.1.4. Hypothesis Testing and Significance Level

Not applicable.

7.3.1.5. Sensitivity Analyses

There are no planned sensitivity analyses.

7.3.2. Secondary Analyses

Secondary analyses will be performed using the FA Set. The secondary continuous endpoints (Cu balance, Mo balance, urinary excretion, etc.) will be analyzed using the same methods described for the primary analysis. The periods of interest described in Section 7.3 will be utilized as appropriate. The daily Cu and Mo balances for each participant will be plotted, as will the mean daily Cu and Mo balances.

7.3.3. Exploratory Analyses

The exploratory endpoint analyses will be conducted on the FA Set. The exploratory endpoints will be analyzed in the same manner as the primary endpoint. Additionally, plasma Cu:Mo ratio and Cu:Mo ratio in urine and feces will be examined. The ratios will be derived at the participant level daily and then summarized. The periods of interest described in Section 7.3 will be utilized as appropriate.

To improve the understanding of the effects of ALXN1840 treatment duration, individual periods may be sub-segmented. For example, Day 1 through Day 15 may be divided into Day 1 through Day 5, Day 6 through Day 10, and Day 11 through 15 to assess Cu output early following treatment, in the middle of the Treatment Period and at the end of the Treatment Period.

7.4. Safety Analyses

All safety analyses will be made on the Safety Set.

Safety analyses will include all AEs, ECGs, clinical laboratory data, physical examinations, and vital sign measurements using descriptive statistics.

No inferential statistical analyses are planned for the safety parameters of this study.

7.4.1. Study Duration, Treatment Compliance, and Exposure

Study duration will be summarized for all enrolled participants by group and overall. Study duration is defined as the time from first dose to the EOS or study discontinuation date (whichever occurs first) + 1.

Compliance to the study treatment regimen will be determined as the days taken / the days expected to be taken during the treatment period x 100. Treatment compliance will be summarized using descriptive statistics by group. If a patient discontinues prematurely from the study, his or her compliance will be based on the period up to the point of discontinuation from the study. Compliance will also be summarized using counts and percentages by compliance category (i.e., $\geq 100\%$ compliance, 80 to $<100\%$ compliance, 60 to $<80\%$ compliance, etc.).

Exposure will be summarized for the Safety Set by group and overall. The duration (days) of exposure to treatment will be calculated as date of last exposure to treatment – date of first dose + 1. The actual duration of treatment will be calculated as the exposure period – number of days on which treatment was temporarily stopped. The duration of exposure, average daily dose (mg), minimum daily dose (mg) and maximum daily dose (mg) will be summarized using descriptive statistics. A supportive listing will also be provided.

7.4.2. Adverse Events

The verbatim terms as reported in the CRF by Investigators to identify AEs will be coded using the MedDRA, Version 22.0 or higher and summarized by primary SOC and PT.

Adverse event toxicity will be evaluated using the NCI CTCAE Version 5.0 (published 27 Nov 2017).

Adverse event causality is determined by the Investigator using the following assessment categories: unrelated, or related.

Treatment-emergent AEs are defined as those AEs with onset on or after the first dose of treatment (ie, study drug). Events reported with a partial onset date (eg, month and year are reported but the day is missing) will be considered to be treatment-emergent if it cannot be confirmed that the event onset was prior to the first dose of study drug based on the available date entries.

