### 10.3. Appendix 3: Adverse Events: Definitions and Procedures for Recording, Evaluating, Follow-up, and Reporting

#### 10.3.1. Definition of AE

AE Definition

 
An AE is any untoward medical occurrence in a participant, temporally associated with the use of study intervention, whether or not considered related to the study intervention.
 
Note: An AE can therefore be any unfavorable and unintended sign (including an abnormal laboratory finding), symptom, or disease (new or exacerbated) temporally associated with the use of study intervention.
 

Events Meeting the AE Definition

 
Any abnormal laboratory test results (hematology, clinical chemistry, or urinalysis) or other safety assessments (eg, ECG, radiological scans, vital signs measurements), including those that worsen from baseline, considered clinically significant in the medical and scientific judgment of the Investigator.
 
Exacerbation of a chronic or intermittent pre-existing condition including either an increase in frequency and/or intensity of the condition.
 
New conditions detected or diagnosed after study intervention administration even though it may have been present before the start of the study.
 
Signs, symptoms, or the clinical sequelae of a suspected drug-drug interaction.
 
Signs, symptoms, or the clinical sequelae of a suspected overdose of either study intervention or a concomitant medication. Overdose per se will not be reported as an AE/SAE unless it is an intentional overdose taken with possible suicidal/self-harming intent. Such overdoses should be reported regardless of sequelae.
 

Events Not Meeting the AE Definition

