
 
Medical or surgical procedure (eg, endoscopy, appendectomy): The condition that leads to the procedure is the AE. Situations in which an untoward medical occurrence did not occur (eg, hospitalization for elective surgery if planned before the signing the ICF, admissions for social reasons or for convenience).
 
Anticipated day-to-day fluctuations of pre-existing disease(s) or condition(s) present or detected at the start of the study that do not worsen.
 
A medication error (including intentional misuse, abuse, and overdose of the product) or use other than what is defined in the protocol is not considered an AE unless there is an untoward medical occurrence as a result of a medication error.
 
Cases of pregnancy that occur during maternal or paternal exposure to study intervention are to be reported within 24 hours of Investigator/site awareness. Data on fetal outcome and breastfeeding will be collected for regulatory reporting and safety evaluation.
 
Situations in which an untoward medical occurrence did not occur (social and/or convenience admission to a hospital).
 

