**Follow-up of AEs and SAEs**

- The Investigator is obligated to perform or arrange for the conduct of supplemental measurements and/or evaluations as medically indicated or as requested by Alexion to elucidate the nature and/or causality of the AE or SAE as fully as possible. This may include additional laboratory tests or investigations, histopathological examinations, or consultation with other health care professionals.
- If a participant dies during participation in the study or during a recognized follow-up period, the Investigator will provide Alexion with a copy of any post-mortem findings including histopathology.
- New or updated information will be recorded in the originally completed CRF.
- The Investigator will submit any updated SAE data to Alexion within 24 hours of receipt of the information.

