5.3.1. Adverse Events

All AEs will be reported to the Investigator or qualified designee by the participant (or, when appropriate, by a caregiver, surrogate, or the participant's legally authorized representative).

All AEs and SAEs will be collected from the signing of the informed consent form (ICF) until the End of Study (EOS) Visit.

Each AE will be characterized (ie, verbatim term) and information regarding its seriousness, start and stop dates, toxicity, outcome, and causal relationship with the study drug will be provided. The safety evaluation will include an assessment of all AEs, SAEs, AE toxicity, and AE relatedness to study drug. Adverse event toxicity will be evaluated using the National Cancer Institute (NCI) Common Terminology Criteria for Adverse Events (CTCAE) Version 5.0 (published 27 Nov 2017) ([NCI, 2017](#)). Further details are given in the [Protocol Section 8.3](#) and [Protocol Appendix 3](#).

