7.4.2.1. Overall Summary of Adverse Events

An overall summary of TEAEs will be presented, including number of events and number and percentage of participants experiencing AEs. Percentage will be calculated as $n/N \times 100$, where n is the number of participants with events and N is the number of participants in the Safety Set. The summary will include categories indicating how many events are TEAEs, treatment-emergent SAEs, and treatment-emergent non-SAEs. Within TEAEs, the following subcategories will also be summarized:

- Toxicity of TEAEs (Grade 1 through Grade 5)
- Related TEAEs (not related, related)
- TEAEs leading to withdrawal of study drug
- TEAEs leading to withdrawal from the study
- TEAEs leading to death

A summary of events (E) and number of participants with events (n , %) for pre-treatment adverse events (PTAEs) will also be included with its relevant subcategories.

A listing of all TEAEs by participant will be presented. Separate listings will be produced for SAEs, AEs leading to study drug withdrawal, AEs resulting in death, AEs leading to withdrawal from the study and PTAEs.

7.4.2.2. Adverse Events and Serious Adverse Events by System Organ Class and Preferred Term

The number of TEAEs and the number and percentage of participants with events will be presented by SOC and PT. Participants are counted once in each SOC and PT. Percentages will be based on the Safety Set. The SOCs will be listed in alphabetical order and PTs within each SOC will be listed by descending frequency. If needed, PTs will also be ordered alphabetically.

Treatment-emergent SAEs, treatment-emergent non-SAEs, TEAEs leading to withdrawal of study drug, TEAEs leading to withdrawal from the study, TEAEs leading to death, and PTAEs will be summarized using the same approach.

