9.2. Technical Specifications for Derived Variables

9.2.1. Adverse Events

The analysis of AEs is described in detail in Section 7.4.2.

Treatment-emergent AEs are events with start dates and start times on or after the date and time of the first study drug dose. If the start date of an AE is partially or completely missing and the end (stop) date and time of the AE does not indicate that it occurred prior to first dose, then the determination of treatment-emergent status will be based on the following:

- If the start year is after the year of the first study drug dose, then the AE is treatment-emergent; else,
- If the start year is the same as the year of the first study drug dose and
 - the start month is missing, then the AE is treatment-emergent; else if
 - the start month is present and is the same or after the month of the first study drug dose, then the AE is treatment-emergent; else,
- If the start date is completely missing, then the AE is treatment-emergent.

All other AEs are considered PTAEs (ie, AEs with partial or complete start dates before first study drug dose).

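### The SAP classes an AE as treatment-emergent by its start date and time alone, so a pre-dose AE kept as one record that worsens on ALXN1840 is tabulated as pre-treatment

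*SAP*

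**What the plan says.** The definition in SAP 7.4.2 rests on onset: "Treatment-emergent AEs are defined as those AEs with onset on or after the first dose of treatment (ie, study drug". SAP 9.2.1 turns this into a comparison of start date and time with the date and time of first dose, and closes with a residual rule: "All other AEs are considered PTAEs (ie, AEs with partial or complete start dates before first study drug dose". The other rules in both sections deal only with partial or missing dates. The protocol uses the term TEAE but gives no definition of its own.

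Three other places bear on how a worsening event reaches the analysis data:

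- **Updates.** Protocol 10.3.3, on follow-up: "New or updated information will be recorded in the originally completed CRF".
- **Fields.** SAP 5.3.1 says that for each AE "information regarding its seriousness, start and stop dates, toxicity, outcome, and causal relationship with the study drug will be provided". No dated change of grade is listed.
- **AE definition.** Protocol 10.3.1 lets an AE be a sign, "symptom, or disease (new or exacerbated) temporally associated with the use of study intervention". It also counts worsening, in frequency or intensity, of a chronic or intermittent condition that was already present. What it excludes is "Anticipated day-to-day fluctuations of pre-existing disease(s) or condition(s) present or detected at the start of the study that do not worsen".

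**The concern.** AEs are collected from consent (Protocol 8.3.1), screening opens on Day -35 and participants are resident from Day -8. An AE can therefore be open when dosing starts on Day 1. If it worsens on drug and the site updates the existing entry, the start date stays before first dose, and the SAP files the event as pre-treatment whatever grade it reaches.

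A mild gastrointestinal complaint during the run-in diet is a realistic example. Protocol 4.3 names such complaints among the common AEs in the oncology programs, and no laboratory shift table would show the change.

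At stake is whether the TEAE tables of the first repeat-dose study in healthy participants depend on a recording habit that neither document fixes. The rule also runs against the SAP's own conventions. A completely missing start date makes an AE treatment-emergent (9.2.1), a missing relationship is taken as related (7.4.2.5), and a missing toxicity is taken as Grade 3 (7.4.2.6). A known worsening on drug is the case that is resolved the other way.

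**Working it through.** The plan gives no figure to reproduce on this point. The check traces the rule on an assumed event and then sizes the effect.

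**Trace.** Assumed event: starts Day -3 at Grade 1, first dose Day 1, reaches Grade 3 or becomes serious on Day 6.

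| How it is recorded | Start date seen by SAP 9.2.1 | Class |
|---|---|---|
| One record, updated | Day -3 | PTAE |
| Pre-dose record closed, new record at worsening | Day -3 and Day 6 | PTAE and TEAE |
| One record, start date completely missing, stop date not before dosing | none | TEAE |

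**Where the one-record event goes.**

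- *Absent from:* the TEAE and treatment-emergent SAE summaries (SAP 7.4.2.1, 7.4.2.2), the SOC-only and PT-only tables (7.4.2.3, 7.4.2.4), the relationship and related-TEAE tables (7.4.2.5) and the toxicity tables (7.4.2.6). All of these count TEAEs.
- *Present in:* the PTAE summary, its SOC/PT table and its listing. SAP 7.4.2.1 also says "Separate listings will be produced for SAEs, AEs leading to study drug withdrawal, AEs resulting in death", with a further listing for study withdrawals, and does not restrict these to TEAEs. Laboratory worsening also appears in the shift tables (7.4.3.1).

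**Size per affected participant.** Change in a row percentage = 1/N, where N is the table's denominator.

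- Overall, Safety Set of about 17 (Protocol 9.2): 1/17 = 0.0588, or 5.9 percentage points.
- First group, about 6 and at most 8 (Protocol 4.1): 1/8 = 12.5 points and 1/6 = 16.7 points.

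The group figures apply only to tables shown by group. SAP 7 presents analyses by group and overall where specified. SAP 7.4.2.3 and 7.4.2.4 take percentages from the treatment cohort, while 7.4.2.2 uses the Safety Set.

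The lower limit is 0. SAP 7.4.2.2 states "Participants are counted once in each SOC and PT", so the row percentage does not move if the participant has another qualifying event in that row. It also does not move if the site opened a new record. The number of events in the row still falls by one whenever a single record is misfiled.

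**Can the data show the worsening?** With the SAP 5.3.1 fields, a record updated from Grade 1 to Grade 3 need not show when the grade rose, or that it rose at all. A clause based on grade increase therefore cannot be programmed from those fields for a single record. A new record at worsening carries its own start date and needs no extra field.

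**The case against.** The strongest reply is that separate recording is the better-supported reading of the protocol. Under Protocol 10.3.1 an exacerbation can itself be an AE. Its onset would then be after first dose, and the present SAP wording would make it a TEAE. The sentence in 10.3.3 on updates says where information is written, not that a worsened event keeps its old start date. The CRF completion instructions may already call for a new entry.

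Much of this stands. It shows that the one-record case is permitted rather than required, and that the harm is conditional. It does not close the gap. The exacerbation bullet concerns chronic or intermittent pre-existing conditions and does not say that an AE already on the CRF is split when it worsens. Neither document gives that instruction.

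A reader might infer more than the documents support:

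- *That such events vanish from the report.* They do not. They stay in the PTAE outputs and, where applicable, in the unrestricted listings.
- *That the stopping rules could miss them, because Protocol 6.6.1 defines an adverse reaction as a related TEAE.* Nothing ties those rules to the SAP's date algorithm. The liver, hematology and QT rules for individuals (6.6.1.4) rest largely on measured values, and the SRC reviews all AEs (9.7).
- *That 5.9 points is a ceiling.* It holds for the overall denominator only.

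**Conclusion.** The point holds, conditionally, and is minor. The SAP states a rule that puts on-drug worsening of a single-record, pre-dose AE under a pre-treatment heading and out of the TEAE-based tables.

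The conclusion rests on two assumptions: that at least one AE starts before dosing, is open at Day 1 and worsens on drug, and that the site keeps it as one record. The documents give no basis for a frequency. It is probably low, since participants are screened healthy and all of these conditions must hold together. Safety analysis is descriptive, and the primary endpoint, the stopping rules and SRC review are unaffected.

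**What to change.** **SAP wording.** In 7.4.2 and 9.2.1, define a TEAE as an AE with onset on or after first dose, or with onset before it and an increase in CTCAE grade or seriousness on or after it. Limit the PTAE rule in 9.2.1 to AEs that meet neither condition.

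**Recording.** This is the part that makes the definition work. If no such instruction exists, add to the CRF completion instructions that post-dose worsening is entered as a new AE dated at the change, with the pre-dose record closed at its pre-dose grade. The event then counts once on each side of first dose.

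**Single records left at database lock.** Find worsening by data review, through a site query or the CRF audit trail. If worsening is confirmed but its date stays unknown, count the event as a TEAE at its highest grade, in line with the SAP's other conservative rules.

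**Cost.** Edits to two SAP sections, one instruction, a little programming and a small amount of query work. No protocol amendment is needed. TEAE counts may be slightly higher, and the unknown-date rule may take in some worsening that happened before dosing.

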7.4.2.1. Overall Summary of Adverse Events

An overall summary of TEAEs will be presented, including number of events and number and percentage of participants experiencing AEs. Percentage will be calculated as $n/N \times 100$, where n is the number of participants with events and N is the number of participants in the Safety Set. The summary will include categories indicating how many events are TEAEs, treatment-emergent SAEs, and treatment-emergent non-SAEs. Within TEAEs, the following subcategories will also be summarized:

- Toxicity of TEAEs (Grade 1 through Grade 5)
- Related TEAEs (not related, related)
- TEAEs leading to withdrawal of study drug
- TEAEs leading to withdrawal from the study
- TEAEs leading to death

A summary of events (E) and number of participants with events (n , %) for pre-treatment adverse events (PTAEs) will also be included with its relevant subcategories.

A listing of all TEAEs by participant will be presented. Separate listings will be produced for SAEs, AEs leading to study drug withdrawal, AEs resulting in death, AEs leading to withdrawal from the study and PTAEs.

7.4.2.2. Adverse Events and Serious Adverse Events by System Organ Class and Preferred Term

The number of TEAEs and the number and percentage of participants with events will be presented by SOC and PT. Participants are counted once in each SOC and PT. Percentages will be based on the Safety Set. The SOCs will be listed in alphabetical order and PTs within each SOC will be listed by descending frequency. If needed, PTs will also be ordered alphabetically.

Treatment-emergent SAEs, treatment-emergent non-SAEs, TEAEs leading to withdrawal of study drug, TEAEs leading to withdrawal from the study, TEAEs leading to death, and PTAEs will be summarized using the same approach.

7.4.2.3. Adverse Events s by System Organ Class

The number of TEAEs and the number and percentage of participants with events will be presented by SOC only. Participants are counted once in each SOC. Percentages will be based on the total number of treated participants in the treatment cohort.

7.4.2.4. Adverse Events by Preferred Term

The number of TEAEs and the number and percentage of participants with events will be presented by PT only. Participants are counted once for each PT. Percentages will be based on the total number of treated participants in the treatment cohort.

7.4.2.5. Adverse Events and Serious Adverse Events by System Organ Class, Preferred Term, and Relationship

The number of TEAEs and the number and percentage of participants with events will be presented by SOC and PT as described in Section 7.4.2.2 by relationship (related, not related). If a participant has more than 1 occurrence of an AE, the strongest relationship to study drug will be used in the summary table. If relationship to study drug is missing, the AE will be assumed to be related. A similar analysis will be conducted for treatment-emergent SAEs.

The number of related TEAEs and the number and percentage of participants with related TEAEs will be summarized by SOC and PT, and separately by PT only. The same analyses will be produced for related treatment-emergent SAEs.

Lastly, the number of TEAEs by SOC, PT, and relationship, without taking into account the highest relationship, will be analyzed. A similar analysis will be conducted for treatment-emergent SAEs.

7.4.2.6. Adverse Events and Serious Adverse Events by System Organ Class, Preferred Term, and Toxicity

The number of TEAEs and the number and percentage of participants with events will be presented by SOC, PT and toxicity (ie, CTCAE grade). If a participant has more than 1 occurrence of an AE, the highest toxicity reported will be used. If toxicity is missing, the AE will be assumed to be Grade 3 (ie, severe). The number of TEAEs by SOC, PT, and toxicity, without taking into account the highest toxicity, will also be analyzed.

Additionally, a summary of related TEAEs by SOC, PT, and toxicity using the highest toxicity will be presented.

7.4.3. Other Safety

7.4.3.1. Analyses for Laboratory Tests

Actual values and changes from treatment Baseline (eg, chemistry, blood cell count with differential, and urinalysis) will be summarized descriptively for participants with available data for each laboratory parameter by group and overall. Missing laboratory data will not be imputed and only scheduled assessments will be included in by-visit summaries. All data, including that which is only collected at Screening, will be included in data listings. Laboratory measurements will be listed separately by participant, laboratory test, unit, and visit.

Where applicable, laboratory results will be classified as “low,” “normal,” or “high” with respect to the parameter-specific reference ranges (ie, below the lower limit of the normal range, within the normal range, or above the upper limit of the normal range). Contingency tables will be presented for each laboratory parameter to summarize the shift from the Baseline category to all

visits and to the worst post-Baseline measurement, defined as the value numerically farthest outside of the normal range across all post-Baseline visits through the end of the study.

Summary results for shift will include the count and percentage of participants within each shift category by scheduled visit. Laboratory values outside the normal range will also be summarized and assessed for trends indicating a safety signal. Additionally, a summary and listing of liver enzyme elevation will be presented and an evaluation of drug-induced serious hepatotoxicity plot will be created.

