**Table 3: Potential Risks and Mitigation Strategy**

Potential Risk of Clinical Significance	Summary of Data/Rationale for Risk	Mitigation Strategy
ALXN1840		
Dose-dependent elevations in transaminases (ALT and AST)	Generally mild to moderate in severity, asymptomatic and reversible with dose adjustments were reported, usually after 3-6 weeks of treatment. Results obtained from studies of ALXN1840 and ammonium tetrathiomolybdate in patients with WD; see the IB	Regular monitoring of liver function tests. Dose modification or discontinuation ( Section 6.6 )
Anemia	Anemia has been observed in patients with WD, attributed to overtreatment and resultant Cu depletion, see the IB	Monitoring complete blood count. Dose modification or discontinuation ( Section 6.6 )
Low white blood cell count (leukopenia, bone marrow toxicity)	Leukopenia and bone marrow toxicity (myelosuppression) have been observed in patients with WD, attributed to overtreatment and resultant Cu depletion. Results obtained from studies of ALXN1840 and ammonium tetrathiomolybdate in patients with WD; see the IB	Monitoring of complete blood count. Dose modification or discontinuation ( Section 6.6 )
Neurological dysfunction	Neurological worsening may occur due to Cu mobilization. Peripheral neuropathy may be seen with over-decuppering; however, symptoms such as myelosuppression is typically seen earlier	Neurologic dysfunction is not anticipated in HV population.
Study Procedures		
Risks associated with the study design and procedures	Participants will undergo repeated blood draws to measure the PK of the study intervention and metabolism. Blood draws may result in ecchymosis, redness and minor pain to the site. On rare occasion, infection or thrombophlebitis can occur	Blood draws are optimized for PK. A cannula may be placed to minimize needle sticks; however, a catheter may not be left in place for longer than 72 hours, and should be flushed a minimum of every 8 hours

Abbreviations: ALT = alanine aminotransferase; AST = aspartate aminotransferase; Cu = copper; IB = Investigator's Brochure; PK = pharmacokinetics; WD = Wilson Disease.

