## **6.6. Dose Modification**

Asymptomatic elevations of hepatic transaminases and gamma glutamyltransferase have been reported in patients with WD treated with ALXN1840 and have occasionally been seen in ALXN1840 single dose studies in healthy volunteers, and in published data from oncology studies. Liver enzymes will be monitored a minimum of every 3 days throughout the study. In addition, chronic treatment with ALXN1840 may result in anemia, leukopenia or thrombocytopenia due to over-decuppering. As this is the first repeat-dose study to be conducted in healthy participants, complete blood count with platelets will also be monitored a minimum of every 3 days. Ceruloplasmin concentrations will be measured and may be used as appropriate to guide group dosing decisions.

If laboratory tests result in abnormal values, it will be expected that the tests are repeated to confirm those results. Depending on the severity of the abnormal values, laboratory tests may be checked as frequently as daily; it is at the discretion of the Investigator to track abnormal values. Results from non-scheduled safety laboratory assessments must be recorded in the CRF.

Alexion should be notified within 24 hours of any laboratory, vital sign, ECG abnormality or AE that are considered of clinical concern by the Investigator. Investigators must notify Alexion immediately of drug discontinuation. The decision to discontinue drug should not be delayed for causality assessment.

Following dosing of the first group of approximately 6-8 participants, if ceruloplasmin concentrations or AE findings are suggestive of Cu depletion, the SRC ([Section 9.7](#)) may reduce the dose to 15 mg/day for the remainder of the study population.

Dose modification guidelines will be specified as follows.

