#### **9.4.2. Safety Analyses**

All safety analyses will be made on the Safety Set.

Safety analyses will include all AEs, ECGs, clinical laboratory data, physical examinations, and vital sign measurements using descriptive statistics.

No inferential statistical analyses are planned for the safety parameters of this study. The incidence of AEs and SAEs will be summarized by System Organ Class and Preferred Term for each treatment and overall, and by relationship to study intervention. Adverse events will also be summarized by treatment and overall by severity. Serious AEs and AEs resulting in withdrawal from the study will be listed. Participants having multiple AEs within a category (eg, overall, System Organ Class, Preferred Term) will be counted once in that category. For severity tables, a participant's most severe event within a category will be counted.

Changes from baseline in vital sign measurements and laboratory assessments (eg, chemistry, blood cell count with differential, and urinalysis) will be summarized by treatment. Laboratory parameter values will be graded according to the National Cancer Institute CTCAE. Shift tables by treatment will be produced for these laboratory parameters. These tables will summarize the number of participants with each baseline grade relative to the reference ranges and changes to the worst highest grade assessed post-dose during the study.

ECG parameters will be measured at the specified time points as per the SoA (Table 1), including heart rate, PR, RR, QRS, QT, and QTcF intervals. The average of the triplicate ECG

readings at the time points collected will be calculated, and changes from pretreatment baseline values will be assessed by each treatment.

All concomitant medications will be coded and summarized using the World Health Organization (WHO) Drug Dictionary.

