4.1. Changes From Analyses Specified in the Protocol

Not applicable. There are no changes from the protocol.

4.2. Changes From Analyses Specified in the Previous Version of the Statistical Analysis Plan

Not applicable. This is the first version of the SAP.

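### SAP 7.4.3.1 drops the protocol's CTCAE-grade laboratory shifts without declaring it, and its direction-free worst value can class a participant with a low count as high in that one table

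*SAP*

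**What the plan says.** Protocol 9.4.2 (Safety Analyses) sets the laboratory summary: "Laboratory parameter values will be graded according to the National Cancer Institute CTCAE. Shift tables by treatment will be produced for these laboratory parameters". Those tables are to show each baseline grade and "changes to the worst highest grade assessed post-dose during the study".

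SAP 7.4.3.1 specifies something different. Where applicable, "laboratory results will be classified as “low,” “normal,” or “high” with respect to the parameter-specific reference ranges". Contingency tables then set the baseline category against all "visits and to the worst post-Baseline measurement, defined as the value numerically farthest outside of the normal range across all post-Baseline visits". The section does not mention CTCAE. Elsewhere the SAP applies CTCAE only to adverse events (SAP 5.3.1, 7.4.2 and 7.4.2.6). SAP 4.1, on changes from the protocol's analyses, reads: "Not applicable. There are no changes from the protocol".

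The hematologic risks that the protocol names are all in the low direction. Table 3 states: "Leukopenia and bone marrow toxicity (myelosuppression) have been observed in patients with WD, attributed to overtreatment and resultant Cu depletion". Section 6.6 adds that "chronic treatment with ALXN1840 may result in anemia, leukopenia or thrombocytopenia due to over-decuppering", and Section 4.3 lists neutropenia and lymphocytopenia among the myelosuppressive effects reported in oncology programs.

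**The concern.** There are two separate issues in the same paragraph of the SAP.

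The first is a departure from the protocol that is not declared. A low/normal/high table records direction but not severity. The protocol ties its own platelet suspension limit, and its margin on hemoglobin, to CTCAE Grade 2 (Section 6.6.1.4), and its group rules to Grades 2 and 3 (Sections 6.6.1.3 and 6.6.1.5). Without laboratory grades, no hematology shift table uses the scale on which the protocol judges these events.

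The second is the worst-value rule. It keeps one value per participant and parameter, chosen by numerical distance outside the range, and names no direction. A count cannot fall below zero, so its distance below the range is at most LLN. Its distance above the range has no such limit. For blood counts the rule therefore leans toward high values, while the risk of interest is low ones. At stake is whether the worst-value shift table describes hematologic safety correctly in what the protocol calls the first repeat-dose study in healthy participants.

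**Working it through.** **Text comparison (no assumption needed).**

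- Scale: CTCAE grade in Protocol 9.4.2; low, normal or high in SAP 7.4.3.1.
- Post-dose summary: highest grade in the protocol; value farthest outside the range in the SAP.
- Declared change: none in SAP 4.1.

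So the grade-based laboratory shift is missing and the omission is undeclared. As an example of what is lost, assume a platelet LLN of 150 x10^9/L. Counts of 149 and 74 both fall in the low cell, although 74 lies below the limit of 75,000/mm3 (75 x10^9/L) that Protocol 6.6.1.4 defines as Grade 2 or higher.

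**Worst-value rule.** There is no stated figure to reproduce, so the rule is applied literally:

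- Distance of a value v = max(LLN - v, v - ULN, 0). The worst value is the one with the largest distance.
- A low value x has distance LLN - x. A high value h has distance h - ULN. The high value wins when h > ULN + (LLN - x).
- With x at its floor of zero, any value above ULN + LLN outranks every possible low value.

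The documents give no reference ranges for these counts. The ranges below are assumptions, varied to show sensitivity (all x10^9/L).

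| Count | Assumed range | Low value x | LLN - x | Displaced by any value above | As multiple of ULN |
|---|---|---|---|---|---|
| Leukocytes | 4.0-11.0 | 2.5 | 1.5 | 11.0 + 1.5 = 12.5 | 1.14 |
| Leukocytes | 3.5-10.0 | 2.5 | 1.0 | 10.0 + 1.0 = 11.0 | 1.10 |
| Neutrophils | 2.0-7.5 | 1.0 | 1.0 | 7.5 + 1.0 = 8.5 | 1.13 |
| Neutrophils | 1.8-7.7 | 1.0 | 0.8 | 7.7 + 0.8 = 8.5 | 1.10 |
| Neutrophils | 1.5-7.0 | 1.0 | 0.5 | 7.0 + 0.5 = 7.5 | 1.07 |
| Platelets | 150-400 | 74 | 76 | 400 + 76 = 476 | 1.19 |
| Platelets | 140-450 | 74 | 66 | 450 + 66 = 516 | 1.15 |

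With the first leukocyte range, a participant with 6, 2.5, 5 and 12.6 has distances 0, 1.5, 0 and 1.6. The table records 12.6, classed high. With the first platelet range, 250, 74 and 480 give 0, 76 and 80, and the table records 480, classed high. Taking lowest and highest separately keeps 2.5 and 74 visible.

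**The case against.** The strongest reply is that little is actually hidden. SAP 7.4.3.1 also plans by-visit shifts, descriptive summaries of actual values (which include the minimum, SAP 7), a summary of values outside the normal range, and full listings. Blood counts are taken at least every 3 days, so a low count at a scheduled visit appears in that visit's table. A result judged clinically significant becomes an adverse event, is graded by CTCAE and is tabulated by highest grade (Protocol 8.2.4 and 10.3; SAP 7.4.2.6). A platelet count of 74 would trigger the individual suspension rule and a Safety Review Committee meeting (Protocol 6.6.1.4 and 6.6.1.6), neither of which uses this table.

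Most of this stands, and it sets the size of the point. A reader might infer that the SAP could conceal leukopenia or thrombocytopenia from the safety report, or weaken participant protection. The documents do not support that. A reader might also turn one or two misclassified people among about 17 into an error of 6 to 12 percentage points in reported incidence (1/17 = 5.9%, 2/17 = 11.8%). That is only what one or two such people would contribute to a single table. Nothing in the documents says how likely it is that one healthy participant has both a low value and a farther high value of the same parameter.

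The reply does not meet the whole point. By-visit summaries use scheduled assessments only, while Protocol 6.6 expects abnormal tests to be repeated, possibly daily, so a nadir may be unscheduled. If the visit windows of SAP 9.2.8 are applied, the value nearest the target day is kept, not the most abnormal. The out-of-range summary has no stated format, direction or grade. Graded adverse events depend on the investigator's judgment of clinical significance, whereas grading the laboratory values does not.

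It can also be said that Protocol 9.4.2 is loosely worded, since it describes grades relative to reference ranges, and that Section 9.4 leaves elaboration to the SAP. But the sentence "Laboratory parameter values will be graded according to the National Cancer Institute CTCAE" is clear, and leaving out a specified grading is a change, not an elaboration.

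**Conclusion.** The point holds in two parts. The omission of laboratory CTCAE grading and worst-grade shifts, undeclared in SAP 4.1, is certain from the text. It removes severity from every hematology shift table. The displacement of a low value by a high one follows from the SAP rule read literally, with no direction stated. It can occur at highs of about 1.07 to 1.19 times ULN for the low values illustrated, under assumed reference ranges.

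Displacement affects only the worst-value shift table, and only a participant who has both a low value and a farther high value of the same parameter after baseline. Its frequency cannot be estimated from the documents. This is a table-specification fault in a descriptive study that should be corrected. It does not touch the primary endpoint.

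**What to change.** In SAP 7.4.3.1:

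- Restore the Protocol 9.4.2 shift from baseline CTCAE grade to worst post-dose CTCAE grade, by direction for parameters that can be abnormal either way.
- Replace the single worst value with two shifts per parameter, baseline to lowest and baseline to highest post-baseline value, and state that unscheduled values count.
- Keep the by-visit low/normal/high tables.

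If the sponsor prefers not to restore the grade shifts, SAP 4.1 should at least declare and justify the departure.

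The cost is SAP wording and a few extra tables from data already collected.
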